10.6.4 Statistical and Analytical Issues

10.6.4.1 Adjustment for Covariates

The analysis of percent reduction from baseline in the number of cleared treated lesions at 12 weeks after the last DL-PDT treatment (Visit 6) will use an adjustment for the number of baseline AK lesions as described in section 10.6.3.

No other adjustment for covariates is planned for the primary and secondary efficacy analyses.

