### 6.2.1 Phase 3 MAL cream DL-PDT studies

The efficacy and safety of MAL 16.8% cream DL-PDT were compared with MAL 16.8% cream c-PDT in 2 randomized, investigator-blinded, comparative, intra-individual clinical studies conducted in Australia and Europe, in 231 subjects. Subjects were treated on 1 side of the face or scalp with MAL 16.8% cream DL-PDT and on the contralateral side with MAL 16.8% cream c-PDT.

The results of both Phase 3 studies demonstrated that the efficacy of MAL 16.8% cream DL-PDT is similar (noninferior) to MAL 16.8% cream c-PDT for treatment of AK lesions (on the percentage change from Baseline in the number of treated lesions per side at 12 weeks after 1 treatment), and is significantly less painful.

In the Australian study, the percentage change from Baseline in the number of mild treated lesions was 89.2% for DL-PDT versus 92.8% for c-PDT (95% confidence interval [CI] of the mean treatment difference: [-6.8; -0.3], PP population). In the European study, the percentage change from Baseline in the number of total (mild and moderate) treated lesions was 70.1% for DL-PDT versus 73.6% for c-PDT (95% CI of the mean treatment difference: [-9.5; 2.4], PP population).

Methyl aminolevulinate hydrochloride 16.8% cream DL-PDT was almost painless compared with MAL 16.8% cream c-PDT, with a pain score (on an 11-point scale ranging from 0 to 10) of 0.8 versus 5.7 ( $p<0.001$ ) in the Australian study, and 0.7 versus 4.4 ( $p<0.001$ ) in the European study.

In both studies, regardless of whether the weather was sunny or cloudy, similar efficacy was demonstrated.

The maintenance of lesion response rate assessed in the Australian study was high with both treatments for subjects presenting at Week 24 (96% for DL-PDT lesions and 96.6% for c-PDT lesions).

In these two Phase 3 studies, in 231 subjects, local related adverse events (AEs) were reported less frequently on MAL cream DL-PDT than on MAL cream c-PDT treated sides (45.0% and 60.1% of subjects, respectively).

No new local adverse reactions were reported in the 2 MAL DL-PDT Phase 3 studies compared with the already known local adverse reactions with MAL c-PDT. Methyl aminolevulinate hydrochloride DL-PDT was almost painless compared with MAL c-PDT.

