6 EFFICACY AND SAFETY VARIABLES

6.1 Efficacy Variables

6.1.1 Lesion Response

At Visit 2 (before treatment), the Investigator will map the subject's lesions, count them, and report their severity according to criteria based on Olsen (1991) (see Table 2).

At Visits 2b (if applicable), 4, 4b (if applicable) before treatment and at Visit 6/ET, the severity of pre-existing, treated AK lesions that had been identified and treated previously will be recorded. If new AKs develop in the treatment area, they will be recorded, but not treated nor included into the efficacy evaluations.

Table 2 - Lesion Severity Grade Scale

Grade	Severity	Description
Grade 1	Mild	Slightly palpable, better felt than seen
Grade 2	Moderate	Moderately thick, easily felt and seen
Grade 3	Severe	Very thick and/or obvious actinic keratoses

The Investigator will be asked at Visits 2b (if applicable), 4, 4b (if applicable) and 5/ET to identify each lesion treated previously, and the lesion response as a CR or a non-CR, as described in Table 3.

Table 3 - Lesion Response Score

Response	Score	Description
Complete response (CR)	1	Complete disappearance of the lesion, visually and by palpation
Non-complete response (non-CR)	0	Non-complete disappearance of the lesion

If all of the treated lesions in the treatment area are assessed to be CR at 12 weeks after the last DL-PDT session (Visit 6), the subject will be assessed as a subject CR. If any of the treated lesions in the treatment area are assessed to be non-CR, the subject will be assessed as a non-complete responder. Those subjects who are assessed to be CR, i.e., all treated lesions cleared, at Visit 6 will be offered the opportunity to continue in the long-term follow-up study, to assess recurrence of lesions treated.

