10.2.3 Demographic and Baseline Characteristics

Descriptive summaries of the following demographic data and baseline characteristics will be presented by treatment group and overall using the ITT population.

- Age
- Age group
 - ✓ ≤ 39 years old
 - ✓ 40-64 years old
 - ✓ ≥ 65 years old

Statistical Analysis Plan

- Sex
 - ✓ Male
 - ✓ Female
- Ethnicity
 - ✓ Hispanic or Latino
 - ✓ Not Hispanic or Latino
 - ✓ Not Reported
 - ✓ Unknown
- Race
 - ✓ White
 - ✓ Black or African American
 - ✓ Asian
 - ✓ American Indian or Alaska Native
 - ✓ Hawaiian Native or Other Pacific Islander
 - ✓ Other
 - ✓ Multiple
- Fitzpatrick skin type
 - ✓ Type I
 - ✓ Type II
 - ✓ Type III
 - ✓ Type IV
 - ✓ Type V
 - ✓ Type VI
- Fitzpatrick skin type group
 - ✓ Type I, II and III
 - ✓ Type IV, V and VI
- Number of baseline AK lesions of grade 1
- Number of baseline AK lesions of grade 2
- Number of baseline AK lesions
- Classified number of baseline AK lesions
 - ✓ 4-8 AK lesions
 - ✓ 9-12 AK lesions
- Baseline AK grade
 - ✓ Grade 1 (mild) AK
 - ✓ Grade 2 (moderate) AK

All demographic data and baseline characteristics will be listed.

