10.6.1 Analysis of the Primary Endpoint

The hypothesis test for the primary endpoint can be formally defined as follows:

$$\begin{cases} H_0: \Pi_{MAL} = \Pi_{Vehicle} \\ H_a: \Pi_{MAL} \neq \Pi_{Vehicle} \end{cases}$$

where Π_{MAL} is the proportion of subjects achieving a complete response at 12 weeks after the last MAL DL-PDT and $\Pi_{Vehicle}$ is the proportion of subjects achieving a complete response at 12 weeks after the last vehicle DL-PDT.

The hypothesis test for the primary endpoint will be evaluated on the ITT population at the two-sided significance level $\alpha = 0.00125$. Efficacy will be claimed if the between treatment difference on the primary endpoint is statistically significant with a p-value < 0.00125 . This result will provide an acceptable level of evidence of efficacy, in presence of good internal consistency across primary and secondary endpoints in the absence of a second pivotal study.

The proportion of subjects with complete clearance of all AK lesions treated at each post-baseline analysis visit will be summarized descriptively by treatment groups (overall and by analysis centers). The proportion of subjects with complete clearance of all AK lesions treated at 12 weeks after the last DL-PDT (Visit 6) will be analyzed using the Cochran-Mantel-Haenszel (CMH) test stratified by analysis center (see definition in section 10.6.4.4). No continuity correction will be used. The p-value for the treatment comparison (MAL DL-PDT vs. vehicle DL-PDT) will be calculated from the general association statistic of the stratified CMH test. Difference in proportions between treatment groups and the 99.875% and 95% confidence intervals of the difference will be based on the large sample approximation method for binary data and will be calculated using the method described in the Huiping Zhang "Proportion difference and confidence interval based on Cochran-Mantel-Haenszel method in stratified multi-center clinical trial", 2016, PharmaSUG China 2016, Paper 25 [1]. In addition, the proportion of subjects with complete clearance of all AK lesions treated at 12 weeks after the last DL-PDT (Visit 6) for each treatment group will also be presented.

For the primary analysis, all subjects on the ITT population with missing data for the primary endpoint will be classified as non-responders regardless of treatment allocation (see section 10.6.4.2).

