10.6.3 Analysis of Secondary Endpoints

The hypothesis tests for the secondary endpoints can be formally defined as follows:

Statistical Analysis Plan

$$\begin{cases} H_0: \mu_{MAL} = \mu_{vehicle} \\ H_a: \mu_{MAL} \neq \mu_{vehicle} \end{cases}$$

where μ_{MAL} is the mean percent reduction from baseline in the number of cleared treated lesions at 12 weeks after the last MAL DL-PDT treatment (Visit 6) and $\mu_{vehicle}$ is the mean percent reduction from baseline in the number of cleared treated lesions at 12 weeks after the last vehicle DL-PDT treatment (Visit 6) and

$$\begin{cases} H_0: \pi_{MAL} = \pi_{vehicle} \\ H_a: \pi_{MAL} \neq \pi_{vehicle} \end{cases}$$

where π_{MAL} is the proportion of subjects with 75% or greater reduction from baseline in the number of cleared treated lesions at 12 weeks after the last MAL DL-PDT treatment (Visit 6) and $\pi_{vehicle}$ is the proportion of subjects with 75% or greater reduction from baseline in the number of cleared treated lesions at 12 weeks after the last vehicle DL-PDT treatment (Visit 6).

The hypothesis tests for the secondary endpoints will be evaluated on the ITT population at the two-sided significance level $\alpha = 0.00125$. The adjustment for multiple comparisons is described in section 10.6.4.5.

The number of cleared treated lesions at each analysis visit, the reduction from baseline and the percent reduction from baseline in the number of cleared treated lesions at each post-baseline analysis visit will be summarized descriptively by treatment groups (overall and by analysis centers). The percent reduction from baseline in the number of cleared treated lesions at 12 weeks after the last DL-PDT treatment (Visit 6) will be analyzed using an ANCOVA with treatment, analysis center (see definition in section 10.6.4.4) and baseline AK lesion count as fixed effects; the difference in percent reduction between MAL DL-PDT and vehicle DL-PDT, the 99.875% and 95% confidence intervals of the difference and the p-value will be generated from the ANCOVA model.

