10.6.4.2 Handling of Dropouts or Missing Data

For the primary analysis, all subjects on the ITT population with missing data for the primary endpoint will be classified as non-responders regardless of treatment allocation.

For the sensitivity analysis of the primary endpoint and for the analysis of percent reduction from baseline in the number of treated AK lesions, missing data will be imputed using MI (Multiple Imputation) under the Missing At Random (MAR) assumption. The following steps will be followed:

1. For AK lesion count, the missingness pattern in the data will be evaluated. If the pattern is not monotone, the MCMC method of SAS PROC MI will be used to make it monotone. The single chain method will be used, with 200 burn-in iterations and 100 iterations between imputations. The minimum and maximum values for imputed variables will be set to 0 and 12 respectively, in order to force PROC MI to redraw another value for imputation when an intended imputed value is less than the 0 or greater than 12. Imputed values will be rounded to the nearest integer. The seed number will be set to 112199 and fifty (50) imputations will be created.
2. SAS PROC MI will be used for imputing missing values of data with monotone missing pattern. If the MCMC method of step 1 was previously employed, one imputation will be made using each of the fifty (50) MCMC-imputed datasets. If the MCMC method of step 1 was not previously employed, fifty (50) imputations will be created assuming the data are Missing At Random. The seed number will be set to 112199. These imputations will use the following models:
 - a. For binary outcome, a logistic regression model will be used with covariates for treatment and non-missing AK lesion count from earlier scheduled time points including baseline.
 - b. For AK lesion count, a linear regression model will be used with covariates for treatment and non-missing AK lesion count from earlier scheduled time points including baseline. The minimum and maximum values for imputed variables will be set to 0 and 12 respectively, in order to force PROC MI to redraw another value for imputation when an intended imputed value is less than the 0 or greater than 12. Imputed values will be rounded to the nearest integer.
3. The imputed datasets will be analyzed as specified in sections 10.6.1 and 10.6.3.
4. The resulting analysis on the imputed datasets will then be combined to produce a single set of statistics as follows:

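### The percent-reduction ANCOVA adjusts for baseline lesion count but omits baseline lesion grade, which is collected and probably prognostic; the cost is some precision, not validity

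*SAP*

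**What the plan says.** - **ANCOVA.** SAP 10.6.3 states that percent reduction "will be analyzed using an ANCOVA with treatment, analysis center (see definition in section 10.6.4.4) and baseline AK lesion count as fixed effects". Protocol 10.1.3.3 names the same terms. Count is therefore the only baseline patient characteristic in the model; center is the other adjustment term.
- **Other covariates.** SAP 10.6.4.1: "No other adjustment for covariates is planned for the primary and secondary efficacy analyses".
- **Responder endpoints.** Complete response "will be analyzed using the Cochran-Mantel-Haenszel (CMH) test stratified by analysis center" (SAP 10.6.1). The 75% responder endpoint is handled in the same way.
- **Imputation.** For missing lesion counts, "a linear regression model will be used with covariates for treatment and non-missing AK lesion count from earlier scheduled time points including baseline" (SAP 10.6.4.2). The logistic model for the binary outcome has the same covariates.
- **Grade is available.** At Visit 2, before treatment, the investigator is to map the lesions, "count them, and report their severity according to criteria based on Olsen (1991") (SAP 6.1.1). SAP 10.2.3 tabulates the number of Grade 1 lesions and the "Number of baseline AK lesions of grade 2". The only efficacy use of grade is an exploratory subgroup (SAP 10.6.4.8).
- **Earlier results.** Protocol 6.2.1 reports for the Australian study that "the percentage change from Baseline in the number of mild treated lesions was 89.2% for DL-PDT". For mild and moderate lesions together in the European study, the reduction in "treated lesions was 70.1% for DL-PDT versus 73.6% for c-PDT".

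**The concern.** A baseline covariate is useful in an ANCOVA to the extent that it predicts the outcome within arm. Lesion count is an odd choice as the sole one, because the outcome is a proportion of that count. If each lesion clears with a probability that does not depend on how many lesions the subject has, the expected percentage is the same at 4 lesions as at 12.

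Grade is the more natural candidate: thicker lesions plausibly clear less often, and the data will already be in the database. Randomization is stratified by center only, so the design does not balance severity.

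At stake are the width of the 99.875% interval for the first secondary endpoint, its protection against chance imbalance in severity, and the credibility of the missing-at-random imputation that feeds it. This endpoint has some weight, because the plan relies on consistency between primary and secondary endpoints in the absence of a second pivotal study.

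**Working it through.** **1. The plan's own power figure.** Inputs from protocol 10.2: 380 and 190 subjects, 45% vs 15% complete response, two-sided alpha 0.00125, 7% non-evaluable.
- Removing 7% (353.4 vs 176.7 subjects): power 99.999%.
- Counting the 7% as non-responders (0.93 x 45% = 41.85% vs 0.93 x 15% = 13.95%): power 99.997%.
- Both agree with the stated figure of more than 90%. That power needs only 213 subjects, or 213/0.93, about 230, after inflation.
- The larger total comes from the follow-up target: 380 x 0.93 x 0.45 x 0.70 x 0.90 = 100.2 completers.

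A covariate therefore cannot matter for the primary test at the planned effect.

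**2. What count can tell.** With independent lesions clearing with probability p, the expected percentage cleared is 100p at every count n, so count has zero correlation with it. Complete response has probability p^n. At p = 0.892 that is 63% for 4 lesions and 25% for 12. Count thus informs the primary endpoint, where it is not used, and need not inform the percentage, where it is.

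**3. What the earlier results suggest about grade.** The gap between mild lesions and the mild-plus-moderate mix is 89.2 - 70.1 = 19.1 points with daylight and 92.8 - 73.6 = 19.2 points with the lamp. Assume that mild lesions cleared equally in both studies, and let m be the moderate share in the European study, which the documents do not give. Implied moderate clearance = [70.1 - 89.2(1 - m)]/m. Odds ratio = (89.2/10.8) divided by the odds of moderate clearance.

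| m | moderate clearance | odds ratio |
|---|---|---|
| 1.0 | 70.1% | 3.5 |
| 0.8 | 65.3% | 4.4 |
| 0.5 | 51.0% | 7.9 |
| 0.3 | 25.5% | 24 |
| 0.2 | negative | none |

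The direction is clear but the size is not. The assumption breaks down at small m, and m = 1.0 contradicts the description of the lesions as mild and moderate. Odds ratios of 2, 3.5 and 8 are used below as a range, not as estimates.

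**4. Precision gain in the ANCOVA.** Simulation, all inputs assumed except the response rates, arm sizes and lesion range: 4-12 lesions per subject, calibrated to 45% and 15% complete response, within-subject correlation 0.1-0.5, several distributions of the Grade 2 share between subjects, no center effect. Variance = residual variance (MAL)/380 + residual variance (vehicle)/190. Count removes 0.0% of it, by construction, because clearance was made independent of count. For a further reduction R from the Grade 2 share, the interval width shrinks by 1 - sqrt(1 - R) and the equivalent sample size is 570/(1 - R).

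| Grade odds ratio | R | interval narrower by | equivalent N |
|---|---|---|---|
| 2 | 1-4% | 0.5-2% | 576-594 |
| 3.5 | 2-12% | 1-6% | 582-648 |
| 8 | 6-27% | 3-15% | 606-781 |

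A separate simulation assumed per-lesion clearance of 89% (mild) and 60% (moderate) on MAL, 45% and 25% on vehicle, a uniform Grade 2 share and a subject standard deviation of 0.5-2. It gave 3.8-16.6% for grade and 0.0% for count. Its complete-response rates (17-29% and 1-9%) fall below the planning values, so it supports the order of magnitude only.

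**5. The primary risk difference.** Adjusting for Grade 1 and Grade 2 counts together removes about 1-11% of its variance, but the two counts sum to total count. Count alone removes about 2-5%. At odds ratios of 2-3.5, about half or more of the gain is due to count.

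**The case against.** The strongest reply is that nothing here is broken. A center-stratified CMH test and a prespecified ANCOVA are valid under randomization. Omitting a prognostic covariate neither biases the comparison nor inflates type I error, and no power shortfall has been shown for either secondary endpoint. That stands in full. A reader might infer that the planned analysis is biased or underpowered; the documents do not support either.

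A reader might also take odds ratios of 3.5-8 as established. They are not. The two studies differ in region and lesion set, report per-protocol results after one treatment (this trial gives two), and leave the moderate share unstated. The result also depends on how the Grade 2 share varies between subjects, which no document gives.

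Nor do the calculations show that count will be useless in this trial. The 0.0% follows from an assumption; clearance might depend on count in practice.

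Part of the concern is already met. Grade counts are tabulated by arm, so an imbalance would be seen, and effects by grade are planned as a subgroup. The imputation models include earlier post-treatment counts, which carry individual response information, and only 7% of subjects are expected to be non-evaluable. The imputation benefit has not been quantified and is probably small.

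What remains is that a plausible predictor is in hand, an adjusted model is already planned, and the model spends its one patient covariate on the weaker candidate.

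**Conclusion.** The point holds as an optional gain in precision for the percent-reduction endpoint. Across the assumed odds ratios, adding the Grade 2 share takes about 1-27% off the ANCOVA variance. The lower half of that range is the safer expectation, since the odds ratio of 8 rests on a cross-study assumption and a chosen moderate share. For the primary endpoint there is no meaningful gain in power, and much of the available precision would come from lesion count, so the omission of grade should not be blamed for it. Validity, type I error and the primary conclusion are unaffected. Priority: low.

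**What to change.** Before unblinding:

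1. In SAP 10.6.3 and 10.6.4.1, add the baseline share of Grade 2 lesions (Grade 2 count divided by total treated lesions at Visit 2) as a covariate in the ANCOVA, keeping count. A share also avoids having to classify subjects who have both grades, for whom the SAP defines no single baseline grade.
2. In SAP 10.6.4.2, add the same term to the missing-at-random imputation models.
3. Protocol 10.1.3.3 fixes the ANCOVA terms, and 10.1.3.3 and 10.1.6 list the imputation covariates. Make the matching change there, or justify and document it under SAP section 11, which requires an amendment if the blind review changes principal features. A SAP-only edit would leave the two documents in disagreement.
4. Optionally, report a supportive center-stratified, covariate-adjusted risk difference for complete response using Grade 1 and Grade 2 counts. State that at odds ratios of 2-3.5 about half or more of the gain would come from total count.

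The cost is one model term from data already collected, plus a documented change to the protocol's analysis text. If the sponsor prefers to leave the confirmatory ANCOVA alone, a prespecified supportive ANCOVA with grade, together with step 2, secures most of the benefit.

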10.6.4.2 Handling of Dropouts or Missing Data

For the primary analysis, all subjects on the ITT population with missing data for the primary endpoint will be classified as non-responders regardless of treatment allocation.

For the sensitivity analysis of the primary endpoint and for the analysis of percent reduction from baseline in the number of treated AK lesions, missing data will be imputed using MI (Multiple Imputation) under the Missing At Random (MAR) assumption. The following steps will be followed:

1. For AK lesion count, the missingness pattern in the data will be evaluated. If the pattern is not monotone, the MCMC method of SAS PROC MI will be used to make it monotone. The single chain method will be used, with 200 burn-in iterations and 100 iterations between imputations. The minimum and maximum values for imputed variables will be set to 0 and 12 respectively, in order to force PROC MI to redraw another value for imputation when an intended imputed value is less than the 0 or greater than 12. Imputed values will be rounded to the nearest integer. The seed number will be set to 112199 and fifty (50) imputations will be created.
2. SAS PROC MI will be used for imputing missing values of data with monotone missing pattern. If the MCMC method of step 1 was previously employed, one imputation will be made using each of the fifty (50) MCMC-imputed datasets. If the MCMC method of step 1 was not previously employed, fifty (50) imputations will be created assuming the data are Missing At Random. The seed number will be set to 112199. These imputations will use the following models:
 - a. For binary outcome, a logistic regression model will be used with covariates for treatment and non-missing AK lesion count from earlier scheduled time points including baseline.
 - b. For AK lesion count, a linear regression model will be used with covariates for treatment and non-missing AK lesion count from earlier scheduled time points including baseline. The minimum and maximum values for imputed variables will be set to 0 and 12 respectively, in order to force PROC MI to redraw another value for imputation when an intended imputed value is less than the 0 or greater than 12. Imputed values will be rounded to the nearest integer.
3. The imputed datasets will be analyzed as specified in sections 10.6.1 and 10.6.3.
4. The resulting analysis on the imputed datasets will then be combined to produce a single set of statistics as follows:
 - a. For binary outcome, the results from the CMH analysis will be combined using the procedure by Rubin [2] and Li et al. [3] to produce a pooled CMH statistic and p-value. The differences in proportions and standard errors will be combined using the SAS PROC MIANALYZE. The resulting pooled difference and standard error will be used to produce the confidence interval based on the large-sample approximation method for binary data without using continuity correction. Both these methods will be used as described in the Bohdana Ratitch, et al. "Combining Analysis Results from Multiply Imputed Categorical Data", 2013, PharmaSUG Proceedings, Paper SP-03 [4].

Statistical Analysis Plan

- b. For AK lesion count, results from the ANCOVA analysis will be combined using the SAS PROC MIANALYZE.

The number of fifty (50) imputations was selected in order to prevent a power falloff due to choosing a number of imputations too small [5].

As additional sensitivity analysis of the primary endpoint, the multiple imputation process for complete response binary outcome will be repeated based on the Pattern-Mixture Model under the missing not at random (MNAR) assumption, by using the profiles from vehicle DL-PDT subjects with observed data to impute missing data. The process will be the same described for the MAR analysis, only the assumption about missing mechanism will be changed.

The multiple imputation process for complete response binary outcome will be repeated based on the Pattern-Mixture Model under the missing not at random (MNAR) assumption in order to perform a tipping-point analysis for the primary endpoint by varying independently the assumptions about the missing outcomes on the two arms and including scenarios where dropouts on MAL DL-PDT arm have worse outcomes than dropouts on Placebo DL-PDT arm with the aim of exploring the plausibility of missing data assumptions under which the conclusions change (i.e. under which there is no longer evidence of efficacy). The process will be the same described for the MAR analysis, only the assumption about missing mechanism will be changed and points 2, 3 and 4 will be repeated using two independent sequences of shift parameters (one sequence for each treatment arm) that adjust the imputed values for observations in the two treatment arms until the combined results provide no longer evidence of efficacy [6]. The plausibility of the shift parameters under which the conclusions change and, thus, the reliability of the results obtained under MAR assumption will be discussed.

Moreover, the primary analysis will be repeated on the ITT population by imputing missing data using Last Observation Carried Forward (LOCF). If no post-baseline value is available, baseline value will be carried forward.

